7.1 STUDY OUTCOME MEASURES

Primary endpoints:

- number, timing and severity of adverse events in the MSC treatment group will be compared to the placebo group;
- total number of GEL counted over month 1, 3 and 6 will be compared between treatment groups.

[figure not shown]
Secondary endpoints:

- volume of GEL identified over months 1, 3 and 6 will be compared between treatment groups.
- number of GEL counted over months 7, 9 and 12 (crossover re-treatment) compared between treatment periods (placebo vs. active treatment) for each patient.
- combined unique MRI activity (number of new or enlarging T2, or enhancing or re-enhancing lesions).
- number of relapses in MSC treatment group vs. placebo group in the first 6 months and after crossover re-treatment in the two groups (see below for the definition of a relapse).
- time to sustained progression of disability (RRMS group) (see below for definition of sustained EDSS progression) and proportion of progression-free patients.

- proportion of disease-free patients (i.e. patients without relapses) and progression of MRI activity in the two groups.
- changes in the Multiple Sclerosis Functional Composite (MSFC) score in MSC treatment group compared to the placebo group.
- effect of MSCs on the peripheral immune responses (for patients in the first phase of recruitment).
- effect of MSCs on delayed type hypersensitivity (Type 1V hypersensitivity) reaction as measured by the Mantoux test.

Given the exploratory nature of MSC use, no specific quantitative assumptions have been made about the outcomes measures.

[figure not shown]
Figure 1: Patient flow and study outline

7.2 SUBJECT RECRUITMENT

- Patients recruited will have been seen by the Imperial College Healthcare NHS Trust MS service (Figure 2).
- Interested parties who enquired about the trial have been directed to an email address to register their interest: [contact]. Patients have been sent a response described in the 'Stem Cell referrals' standard operating procedure (Appendix 7) to prevent subjects delaying appropriate therapies recommended by their current medical professional.
- When ethical approval is given, subjects will be contacted to determine:
 - Whether they are still interested in taking part
 - Whether they fit the inclusion criteria that can be assessed over the phone
 - Whether they would be able to be referred to Imperial College Healthcare NHS Trust MS service for further evaluation if needed.
- On receipt of a NHS referral letter, the patient will be seen in the NHS clinic for an assessment of their MS. Prior to clinical review by Imperial College Healthcare NHS Trust MS service, subjects will be contacted to provide further details of their MS diagnosis, if not already provided, to consider the likelihood of there being further management options - including all ongoing trials – available to them as a consequence of that review.
- The review by the Imperial College Healthcare NHS Trust MS service will ensure that appropriate investigations have been performed to confirm the diagnosis of MS. Management options – including all available clinical trials – will be discussed with the patient. If appropriate, it will be confirmed that their MS care will be under Imperial College Healthcare NHS Trust otherwise their care will revert solely to their usual medical practitioner.

Figure 2: Patient eligibility selection and flow

Eligibility for the STREAMS study will only be considered at the study screening visit. The inclusion criteria will need to be fulfilled (see section 8.2).

At this visit, they will have a full discussion of the Patient Information Sheet (PIS) and if they consent, will proceed to undergo all study assessments and procedures including bone marrow harvesting (see Figure 4).

8. PARTICIPANT ENTRY

8.1 REFERRAL CRITERIA

All potential study patients need to be referred by a clinician and the referral should include:

1. A current diagnosis of MS.
2. Age 18-50.
3. An assessment of mobility level (preferably EDSS score) documenting EDSS 2.0-6.5 or equivalent mobility.
4. MRI brain and/or spinal cord performed within the last 18 months with findings consistent with MS and showing at least one gadolinium-enhancing lesion (GEL) or one new lesion compared to previous imaging.

Justification for the referral criteria

Criterion 1

Given the experimental nature of the intervention, patients with only one symptomatic episode (diagnosed MS on grounds of paraclinical support) will not be considered.

All patients with clinically defined MS will need to satisfy the revised McDonald criteria.

Criterion 2

The lower limit of age has been set because MS in children is rare and differs significantly from MS in the adult population, and because the study will be carried out in adult (not paediatric) hospital facilities. The upper limit of age has been specified for safety of the experimental cell therapy intervention and to limit the confounding effect of age-related differences in spontaneous lesion repair in the study population.

Criterion 3

A lower Expanded Kurtzke Disability Status Score (EDSS) limit has been specified to ensure that recruited patients have acquired sufficient disability to merit experimental therapeutic approaches. An upper Expanded Kurtzke Disability Status Score (EDSS) limit has been specified to ensure that recruited patients are able to tolerate the trial procedures and assessments.

Criterion 4

This provides a group which will reduce the chance of unnecessary patient testing to meet MRI requirements for the inclusion criteria.

8.2 INCLUSION CRITERIA

Patients with clinically and radiologically active multiple sclerosis as defined by:

1. Diagnosis of MS:
 - a. Relapsing remitting MS (RRMS): ≥ 1 moderate-severe relapse **and** ≥ 1 GEL in past 18 months **or** ≥ 1 moderate-severe relapse and ≥ 1 new T2 lesion in past 18 months.
 - b. Secondary progressive MS (SPMS) with an increase of ≥ 1 EDSS point (if baseline EDSS ≤ 5.0) or 0.5 EDSS point (if baseline EDSS ≥ 5.5), in the previous 18 months **and** ≥ 1 GEL in past 18 months **or** ≥ 1 moderate-severe relapse and ≥ 1 new T2 lesion in past 18 months.
 - c. Primary progressive MS (PPMS) patients with positive oligoclonal bands (OCBs) in the cerebrospinal fluid (CSF) and an increase of ≥ 1 EDSS point (if base-line EDSS ≤ 5.0) or 0.5 EDSS point (if baseline EDSS ≥ 5.5), or quantifiable, objective evidence of equivalent progression in the previous 18 months **and** ≥ 1 GEL in past 18 months or ≥ 1 new T2 lesion in past 18 months.
2. Age 18 to 50 years.
3. Disease duration 0 to 10 years from diagnosis (inclusive).
4. EDSS 2.0 to 6.5 at screening evaluation.
5. ≥ 1 GEL on MRI within 6 months prior to harvesting.
6. Adequate culture of a subject's MSCs and their release for clinical use.

Justification for the inclusion criteria

Working definitions for active MS emphasise accumulation of disability, occurrence of relapses or a combination of both. Our aim is to identify a patient population who is at increased risk of continued progression and loss of function but has not accumulated advanced levels of neuronal injury or degeneration which could fail to show a treatment effect even if it exists. We have therefore formulated criteria to recruit patients with mild to moderate disability and evidence of ongoing inflammation (gadolinium-enhancing lesions) relatively early in the disease.

Each subject must generate MSCs suitable for clinical use otherwise the procedure will have no chance of benefit (section 10.3).

8.3 EXCLUSION CRITERIA

1. RRMS without at least one severe relapse in the previous 18 months or without at least one GEL or one new T2 in the previous 18 months.
2. SPMS without relapses and without new lesions (GEL or T2 positive) on MRI in the last 18 months.
3. PPMS without positive CSF OCBs or without a GEL or new T2 lesion in the previous 18 months.
4. No gadolinium enhancing lesion(s) in the 6 months prior to bone marrow harvesting.
5. A previously ineligible patient who failed to meet the MRI requirements of the inclusion criteria will not be reviewed unless further imaging, revealing ≥ 1 GEL, becomes available.
6. Failure of BM sample to generate MSCs suitable for clinical use within a specified time frame.
7. Treatment with any immunosuppressive therapy, including natalizumab and fingolimod, within the last 3 months.
8. Treatment with interferon-beta or glatiramer acetate within the last 1 month.
9. Treatment with alemtuzumab (campath-1H) within the last 2 years.

10. Prior treatment with total lymphoid irradiation and autologous or allogeneic hematopoietic stem cell transplantation.
11. Participation in clinical trials of any experimental drugs in the 6 months before study entry.
12. Corticosteroid treatment in the previous 30 days.
13. Presence of any active or chronic infection.
14. Previous history of a malignancy other than basal cell carcinoma of the skin and carcinoma *in situ* that has been in remission for more than one year.
15. Severely limited life expectancy by any other co-morbid illness.
16. Abnormal blood counts, a history of myelodysplasia or other cytopenia.
17. Known pregnancy, positive urine pregnancy test at screening or risk or pregnancy (this includes patients who are unwilling to practice active contraception for the duration of the study).
18. Any breastfeeding woman.
19. Contraindication to MRI including but not limited to intracranial aneurysm clips (except Sugita), history of intra-orbital metal fragments that have not been removed by an MD (as confirmed by orbital X-Ray), pacemaker and non-MR compatible devices (e.g. heart valves, inner ear implants), history of claustrophobia or the inability of the subject to lie still on their back for a period of 1.5 hours in the MRI scanner.
20. An estimated glomerular filtration rate (eGFR) $<60 \text{ mL/min}/1.73\text{m}^2$ or history or presence of renal impairment (e.g. serum creatinine clearance less than 30ml/min).
21. Inability to give written informed consent/comply with study procedures.
22. Any significant organ dysfunction or co-morbidity that the Investigators consider would put the subject at unacceptable risk by participating in the study or that would interfere with the functional assessments.

Justification for the exclusion criteria

These criteria are used to exclude MS patients without an active, inflammatory disease and to exclude patients with medical problems or those who are receiving or have received treatments that could increase their risk of serious morbidity or mortality from MSCT or any other facet of this protocol.

8.4 CONCOMITANT MEDICATIONS

All concomitant medications will be recorded at every study visit. Treatment with disease-modifying therapies is not permitted throughout the study – and appropriate wash-out periods are required (see section 8.3) prior to enrolment. Use of corticosteroids will be permitted for relapses that occur during the study although patients cannot have received corticosteroids in the 30 days prior to enrolment. In addition, in the event of a relapse occurring either between randomisation and the first infusion (Week 0) or before the second infusion (Week 24), the infusion will be delayed if the relapse requires the use of corticosteroids, so ensuring that there will be at least 30 days between the methylprednisolone and the infusion. Relapses and the corticosteroids received will be documented on the electronic case report forms.

Symptomatic treatments for MS can be continued throughout the study and may also be initiated if appropriate and at the usual doses. If a patient is already being treated with Fampridine (Fampyra®) at the screening visit, this can be continued but this treatment cannot be initiated during the course of the trial because the effects on walking will affect some clinical endpoints being measured.

Symptomatic treatments for MS permitted in the STREAMS trial (this list may not be exhaustive):

Common Symptoms in MS	Examples of drugs used to treat symptom
Fatigue	Modafinil, amantadine
Depression	Tricyclic antidepressants, monamine-oxidase inhibitors, selective serotonin reuptake inhibitors, other antidepressant drugs.
Spasticity	Baclofen, tizanidine, dantrolene, diazepam, gabapentin, botulinum toxin
Reduced walking ability	Fampridine (Fampyra®)*
Bladder – urinary urgency, frequency and incontinence	Anti-cholinergics (e.g oxybutynin, tolterodine, darifenacin, solifenacin)
Constipation	All types of laxatives
Oscillopsia	Gabapentin, baclofen, clonazepam
Erectile dysfunction	Phosphodiesterase type 5 inhibitors (e.g. sildenafil)

*Fampridine can be continued if it was prescribed before enrolment into the trial but cannot be initiated during the study.

8.5 WITHDRAWAL CRITERIA

Subjects can voluntarily withdraw at any time from the study and follow-up assessments. All data collected up to that point will be retained. Any collected biological specimens will be kept and used for research unless subjects request that these unused samples are destroyed.

A patient's participation in the study may also be discontinued at any time at the discretion of the investigator, and justifiable reasons include Suspected Unexpected Serious Adverse Reactions (SUSAR) or deterioration in the disease activity requiring immunomodulatory treatment but their data until that point will be included in the analysis.

9. RANDOMISATION AND ENROLMENT PROCEDURE

9.1 ELIGIBILITY FOR RANDOMISATION

To be eligible for randomisation a subject must have fulfilled all the entry criteria.

9.2 RANDOMISATION PRACTICALITIES

All subjects will be randomised after the investigator has verified that they are eligible by the criteria (section 8). Randomisation will be carried out within a web-based system, made available to authorised researchers, by the Clinical Research Organisation (CRO) in charge: *Centro Clinical Trials, [contact] Email: [contact]*

Eligible patients will be randomised to receive immediate vs. delayed treatment with either autologous MSCs or equivalent volume of suspension media at baseline. At 6 months, patients and investigators will continue to be blinded to therapy, but treatments will be reversed (i.e. those who received initial MSCs will receive suspension media and vice versa).

9.3 BLINDING PROCEDURES

The patient, assessor team (EDSS, MSFC, MSIS-29, SF36) and MRI team will be blinded to the treatment assignments.

The treating team will not be blinded to treatment assignments. For details about roles, see the Delegation Log.

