9.4.1. Reasons for unblinding

Clinical events: This includes the occurrence of fatal or life-threatening SAE, or any circumstances wherein the judgment of the treating neurologist, blind to the treatment modality, may compromise patient safety or where the patient is unable to provide informed consent to clinically necessary investigations, procedures or treatments as a consequence of the blinding.

MRI findings: Any radiological evidence suggestive of anomalous disease exacerbation or adverse event. This refers to an increase of ≥ 5 number of lesions above the number of lesions on the baseline scan, or the appearance of atypical lesions as assessed by the reviewing radiologist (section 14.1.1). The treating team will be informed as soon as possible.

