11.2 CAUSALITY

Most adverse events and adverse drug reactions that occur in this study, whether they are serious or not, will be expected treatment-related toxicities due to the drugs used in this study. The assignment of the causality should be made by the investigator responsible for the care of the participant using the definitions in the table below. If any doubt about the causality exists, the local investigator should inform the study coordination centre which will notify the Chief Investigator. Other clinicians may be asked to advise in some cases. In the case of discrepant views on causality between the investigator and others, all parties will discuss the case. In the event that no agreement is made, the MHRA will be informed of both points of view.

Relationship	Description
Unrelated	There is no evidence of any causal relationship.
Unlikely	There is little evidence to suggest there is a causal relationship (e.g. the event did not occur within a reasonable time after administration of the trial medication). There is another reasonable explanation for the event (e.g. the participant's clinical condition, other concomitant treatment).
Possible	There is some evidence to suggest a causal relationship (e.g. because the event occurs within a reasonable time after administration of the trial medication). However, the influence of other factors may have contributed to the event (e.g. the participant's clinical condition, other concomitant treatments).
Probable	There is evidence to suggest a causal relationship and the influence of other factors is unlikely.
Definitely	There is clear evidence to suggest a causal relationship and other possible contributing factors can be ruled out.
Not assessable	There is insufficient or incomplete evidence to make a clinical judgement of the causal relationship.

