12.2.2. Unscheduled visits

If subjects have a significant relapse (defined as one which affects the EDSS), an unscheduled visit will need to take place as soon as possible. Minor relapses should be reported at the next scheduled visit. In addition, if adverse effects develop which require clinical evaluation, unscheduled visits will be arranged and patients will be assessed by a treating clinician and managed as medically appropriate.

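### Sections 9.2 and 9.4.1 contradict 9.3 on whether the treating side is blinded, and no blinded role is assigned to elicit or grade adverse events, so detection bias in the primary safety outcome is not excluded

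*Combined protocol and SAP*

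**What the plan says.** The study is titled and designed as double-blind (sections 4 and 7). Three passages then deal with who knows the assignment:

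- Section 9.2, on the period after the crossover: "patients and investigators will continue to be blinded to therapy".
- Section 9.3 lists the blinded parties: "The patient, assessor team (EDSS, MSFC, MSIS-29, SF36) and MRI team will be blinded to the treatment assignments". It continues: "The treating team will not be blinded to treatment assignments". Roles are left to a document outside the protocol: "For details about roles, see the Delegation Log".
- Section 9.4.1, giving a ground for breaking the code, refers to the "judgment of the treating neurologist, blind to the treatment modality".

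On AE work, section 11.2 says: "The assignment of the causality should be made by the investigator responsible for the care of the participant". Section 11.3.2 has the responsible investigator sign the causality of serious events. Section 12.2.2, on unscheduled visits for relapses or adverse effects, says "patients will be assessed by a treating clinician and managed as medically appropriate". For scheduled visits, sections 12.2 and 12.2.1 say that AEs are recorded but not by whom.

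The primary safety endpoint in 7.1 is the number, timing and severity of AEs on MSC against placebo. Section 13.3 compares the number of AEs by a chi-square test.

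**The concern.** Someone who belongs to an unblinded treating team cannot also be a blind treating neurologist, so the protocol as written cannot be followed on this point. The answer matters because AEs are the first-listed primary outcome, and their count and grade depend on how patients are questioned and how events are judged. Section 10.6 even includes an open-ended category of any other toxic effect. Staff who know that cells were infused may ask more closely, record more and grade higher. That would create a difference between arms where none exists, or distort a real one.

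The co-primary lesion outcome is protected, because the MRI team is blinded. The AE outcome has no equivalent protection in the text.

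**Working it through.** **1. The blinding statements side by side.**

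| Section | Who | Status |
|---|---|---|
| 9.2 | Patients and investigators | Blinded |
| 9.3 | Patient, assessor team for four instruments, MRI team | Blinded |
| 9.3 | Treating team | Not blinded |
| 9.4.1 | Treating neurologist | Blind |

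The ground for unblinding in 9.4.1 makes sense only if the treating doctor does not know the assignment. Rows 1 and 4 therefore agree with each other and conflict with row 3.

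**2. Who handles AEs.** Causality goes to the investigator responsible for care (11.2), and unscheduled visits go to a treating clinician (12.2.2). On a plain reading both are on the treating side. Elicitation and grading at scheduled visits are given to nobody by name. The assessor team in 9.3 is defined by its four instruments. The visit lists in 12.2.1 show AEs recorded at weeks 8, 16, 20, 32, 40 and 44, when none of those instruments is scheduled.

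**3. Which AE judgements enter the primary comparison.** The endpoint consists of number, timing and severity, and all AEs are reportable whatever their cause (11.3). Elicitation and grading feed the endpoint. Causality does not; it decides which events count as adverse reactions or SUSARs (11.1).

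**4. Possible size (illustration).** The plan gives no AE rate, so both the base rates and the shifts below are assumptions. The sample sizes come from the plan: 160 pooled, which 13.1 makes the main safety analysis, and up to 23 here (13.2).

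The 160 can be reproduced from 13.2 with a two-sided negative binomial log-rate-ratio formula at 1:1 allocation. Dispersion k = (11.4² − 7.4)/7.4² = 2.238. Then n per arm = (1.960 + 0.842)² × [(1/7.4 + 2.238) + (1/3.7 + 2.238)]/(ln 0.5)² = 7.85 × 4.88/0.480, or 80 after rounding up. This supports using 80 per arm below; the blinding question does not alter it.

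Let p₁ be the recorded share of patients with an AE on placebo, p₂ the share on MSC, and d = p₂ − p₁. With no true difference, the chance of a significant two-sided 5% chi-square test is

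Φ[(d − 1.96 s₀)/s₁] + Φ[(−d − 1.96 s₀)/s₁],

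where s₀² = p̄(1 − p̄)(1/n₁ + 1/n₂), s₁² = p₁(1 − p₁)/n₁ + p₂(1 − p₂)/n₂, and p̄ is the pooled share.

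- 40% to 50%, 80 per arm: p̄ = 0.45, s₀ = 0.0787, s₁ = 0.0783. (0.10 − 0.1542)/0.0783 = −0.69, and Φ = 0.244. The other tail adds less than 0.001.
- 20% to 35%, 12 v 11: p̄ = (12 × 0.20 + 11 × 0.35)/23 = 0.272, s₀ = 0.1857, s₁ = 0.1844. (0.15 − 0.3640)/0.1844 = −1.16, and Φ = 0.123. The other tail adds 0.003, giving 0.126.

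| Assumed shift in recorded share | 80 per arm | 12 v 11 |
|---|---|---|
| 40% to 50% | 24% | 8% |
| 40% to 55% | 48% | 11% |
| 20% to 30% | 31% | 9% |
| 20% to 35% | 57% | 13% |

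The nominal rate is 5%. The table uses the share of patients with at least one AE, whereas the plan speaks of the number of AEs. The normal approximation is rough at 12 v 11.

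**The case against.** The strongest reply is that the text does not show unblinded staff judging AEs. Sections 9.2 and 9.4.1 say the opposite, scheduled AE recording is assigned to no one, and the Delegation Log, which is not among the documents, may limit the unblinded group to those who handle and infuse the product. This stands. A reader might infer from 9.3 and 11.2 together that the primary safety outcome is judged by unblinded staff, but that treats one of two conflicting statements as settled. The log cannot repair the conflict, however, and 9.3 does not define its treating team so narrowly.

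A reader might also infer that unblinded attribution biases the primary comparison. It does not, because causality is not part of that endpoint. Nor do the documents support a claim of unequal discontinuation: 8.5 leaves that decision to the investigator, whom 9.2 calls blinded; each period has one infusion (10.4); and 9.4 keeps patients who stop treatment in follow-up.

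Finally, the larger percentages apply only to the pooled data. At 23 patients the excess over 5% is small, and every figure depends on assumed inputs.

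**Conclusion.** The contradiction between 9.3 and sections 9.2 and 9.4.1 is certain. It is also certain that no section places AE elicitation or severity grading with a blinded role, and that where the text names anyone for AE work it names the treating side. The conclusion is conditional: if 9.3 is what happens in practice, detection bias in the number and severity of AEs is not excluded. Under the assumed rates and shifts, false significance would occur in about 24–57% of pooled analyses and about 8–13% of analyses of this trial alone. These figures show what such a bias could do and are not evidence that it is present. The point should be fixed, but it does not by itself invalidate the design.

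**What to change.** Reword 9.3 to agree with 9.2 and 9.4.1, restricting knowledge of assignment to cell-processing and infusion staff. State in the protocol and in the Delegation Log that the treating neurologist or investigator who elicits AEs and records severity and causality, at scheduled and unscheduled visits alike, is blinded.

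That person should preferably not be the EDSS assessor. Passing AE work to the assessor team would leave the six visits listed above without cover, and could expose the EDSS rater to clues such as infusion reactions. Toxicity recorded on infusion days by unblinded infusion staff should be flagged as such in the data, so that it can be reported separately from blinded AE records.

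The cost is a change of wording and delegation, plus the discipline of keeping infusion staff away from AE assessment. Sample size, treatment and visit schedule are unaffected. Because the main safety analysis is pooled, the other national trials should be asked whether they follow the same rule.
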